1.1 STUDY PROCEDURES

Visit 1, Day -56 to 0 Screening Visit (Up to 8 weeks)

During the screening visit, the subject (or their legally authorized representative as appropriate) and study partner / informant (if not the same as their LAR) will sign the informed consent document prior to undergoing any study procedures.

The following tests and evaluations are used to determine subject eligibility:

- Informed consent
- Inclusion and exclusion criteria
- *CYP2C9* genotyping (buccal swab)
- Medical History & Verify Diagnosis
- Concomitant medication reconciliation
- Serum pregnancy test if applicable
- Neurological and physical examination
- Vital signs, height and weight
- Labs (CBC, CMP, Hep B, Hep C, HIV, TSH)
- Coagulation panel (PT, PTT, INR) (optional, only for patients who opt into LP/CSF substudy)
- Cognitive assessments (MMSE, Hachinski, GDS)
- Columbia Suicide Severity Rating Scale (C-SSRS)
- MRI (MRI or CT within the past 12 months of Screening Visit Day 1)
- EKG (electrocardiogram)

Patients who do not meet the eligibility criteria will not be randomized and will be considered screen failures. Screen failures may be re-screened once per PI discretion for eligibility..

If no MRI or CT scan has been completed within the past 12 months: Participants who consent will be scheduled for volumetric MRI (vMRI) to be completed prior to the Baseline Visit.

In addition, participants will be asked to complete an ophthalmic evaluation to obtain a baseline evaluation prior to the start of treatment.

Optional Lumbar Punctures for CSF Sub-Study

For lumbar punctures, the principal investigator (or sub-investigator) will perform the procedure. A separate section will be added to the consent form, which the subject (or their legally authorized representative) will sign to authorize the lumbar puncture and collection of cerebrospinal fluid (CSF). To ensure subject safety, PT, INR, and PTT levels will be checked at baseline prior to any lumbar puncture procedure and subsequently prior to each follow-up visit where a lumbar puncture is being performed.

A follow-up telephone check will be conducted the day after each lumbar puncture within 24-48 hours. If there is persistent spinal headache, a blood patch may be administered at the discretion of the investigator.

Optional Saliva Sub-Study

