***Do not dose patient on Baseline visit if the patient opted for LP. Refer to Visit 2.5 instead**

- Inclusion/exclusion check
- Concomitant medication reconciliation
- Labs (CBC w/ diff, CMP, TSH)
- Labs (PT, PTT, INR) to be completed and reviewed pre-lumbar puncture for all lumbar punctures
- Optical Coherence Tomography (OCT) Eye Exam (must be done before dose)
- Serum pregnancy test (if applicable)
- EKG (EKG to be completed at pre- and 6-hours post-dose \pm 10 minutes)
- Vital signs including weight
- Vital signs, post-dose, every hour for 6 hours \pm 10 minutes
- Neuro and physical exam
- Cognitive assessments for data collection only (MMSE, ADAS-cog 13, CDR, ADCS-ADL)
- Volumetric MRI (+ 4 weeks window) if vMRI was not completed during Screening
- Blood biomarkers
- Randomization*
- Dispense study drug, patient dose to be completed in-clinic*
- Drug diary provided to patient*
- Drug accountability including instructions on how to take treatment drug*
- Adverse event Assessment

The following are to be completed if participants opted into one, or both, of the optional studies:

- Lumbar puncture followed by phone check in 24hrs-48 hrs post-lumbar puncture
- Saliva collection pre- treatment dose

Visit 2.5 at Day 1 of dosing, Baseline Visit, 0.25mg/day (Only for patients who undergo LP at Baseline)

- Vital signs including weight (pre-dose), hourly vital signs \pm 10 minutes (post-dose observation for 6 hours)
- EKG (pre-dose and post-dose at 6 hours \pm 10 minutes)
- Randomization
- Dispense study drug, patient dose to be completed in-clinic
- Drug diary provided to patient
- Drug accountability including instructions on how to take treatment drug
- Adverse event assessment

Every effort will be made to complete baseline visits in the morning to allow for ample time to monitor participants after the first visit. Subjects will be administered first treatment dose in clinic and will be monitored for the following 6 hours. Every hour subjects will undergo BP/HR monitoring and AE symptom check. Investigator will be notified of BP/HR each hour with HRs rate less than 55 BPM being indicative of immediate intervention by investigator.

At the 6-hour mark after first dose participant will undergo an EKG for safety monitoring. Investigators will review EKG results for bradyarrhythmia and prolonged QT interval. Review of EKG will be completed prior to participant leaving clinic for participant safety.

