Prior to leaving, patients will be given a sufficient supply of study medication (or placebo) to last until the next in-clinic visit at Visit 3 along with instructions for their use. Patients should be instructed to take their medication every morning thereafter at or around the same time.

If a titration dose is missed, or if 4 or more consecutive daily doses are missed during treatment, restart at last dose taken.

Telephone visits at Day 7,21,35,49,63,84,140,196,252, and 308 (± 7 days)

Telephone visits will be used between dose increases to monitor any safety events with participants. In addition, telephone visits will serve as safety check-in.

The following procedures will be performed at all scheduled telephone visits as shown in the schedule of events:

- Medication reconciliation
- AE assessment

Visit 3 at Day 14 (± 7 days) 0.50mg/day

The following tests and procedures will be completed in clinic:

- Concomitant medication reconciliation
- Labs (CBC w/ diff, CMP, TSH)
- EKG (pre-dose, post-dose at 6-hours ± 10 minutes)
- Vital signs including weight (pre-dose)
- Vital signs (post-dose every hour ± 10 minutes for 6 hours)
- Neuro and physical exam
- Blood biomarkers
- Dispense study drug and drug diary
- Drug accountability
- Adverse event assessment

Visit 4 at Day 28 (± 7 days) 0.75mg/day

The following tests and procedures will be completed in clinic:

- Concomitant medication reconciliation
- Labs (CBC w/ diff, CMP, TSH)
- EKG (pre-dose, post-dose at 6-hours ± 10 minutes)
- Vital signs including weight (pre-dose)
- Vital signs (post-dose every hour ± 10 minutes for 6 hours)
- Neuro and physical exam
- Blood biomarkers
- Dispense study drug and drug diary in clinic
- Drug accountability
- Adverse event assessment

Visit 5 at Day 42 (± 7 days) 1 mg/day

The following tests and procedures will be completed in clinic:

- Concomitant medication reconciliation
- Labs (CBC w/ diff, CMP, TSH)
- EKG (pre-dose, post-dose at 6-hours ± 10 minutes)
- Vital signs including weight (pre-dose)

- Vital signs (post-dose every hour \pm 10 minutes for 6 hours)
- Neuro and physical exam
- Blood biomarkers
- Dispense study drug and drug diary in clinic
- Drug accountability
- Adverse event assessment

Visit 6 at Day 56 (\pm 7 days) 1 mg/day

The following tests and procedures will be completed in clinic:

- Concomitant medication reconciliation
- Labs (CBC w/ diff, CMP, TSH)
- EKG
- Vital signs including weight
- Neuro and physical exam

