3. RISK/BENEFIT ASSESSMENT

3.1.1 KNOWN POTENTIAL RISKS

Siponimod (formerly known as BAF312 and completed trial NCT #01665144) has been FDA approved since 2019 (IND #076122) for the treatment of multiple sclerosis. Most adverse events have been reported from MS patients, and very little is known about possible adverse events in subjects without MS. Most risks are associated with doses >2 mg/day. Most common adverse reactions (reported in >5%) are headache, hypertension, and transaminase increase (see Table 2).

Table 2: Summary of Adverse Events Reported in $\geq 5\%$ of Mayzent treated patients at a rate of at least 1% higher than in patients receiving placebo

Adverse reaction	MAYZENT 2 mg (N=1099) %	Placebo (N=546) %
Headache ^a	15	14
Hypertension ^b	13	9
Transaminase increased ^c	11	3
Falls	11	10
Peripheral edema ^d	8	4
Nausea	7	4
Dizziness	7	5
Diarrhea	6	4
Bradycardia ^e	6	3
Pain in extremity ^f	6	4

Terms were combined as follows:

- Headache, tension headache, sinus headache, cervicogenic headache, drug withdrawal headache, and procedural headache.
- Hypertension, blood pressure increased, blood pressure systolic increased, essential hypertension, blood pressure diastolic increased.
- Alanine aminotransferase increased, gamma-glutamyl transferase, increased hepatic enzyme increased, aspartate aminotransferase increase, blood alkaline phosphatase increase, liver function test increased, hepatic function abnormal, liver function test abnormal, transaminases increased.
- Peripheral edema, joint swelling, fluid retention, swelling face
- Bradycardia, sinus bradycardia, heart rate decreased
- Pain in extremity and limb discomfort

POTENTIAL SERIOUS ADVERSE EVENTS

+ *Bradycardia, Bradyarrhythmia, and Atrioventricular Conduction Delays*

Siponimod may cause the heart rate to slow, especially after taking the first dose. This issue will be mitigated by administering an EKG post dose at the 6-hour mark to assess for any potential adverse events. In addition, BP/HR will be checked hourly for 6 hours to assess for potential bradyarrhythmia or adverse events.

+ *Infections*

Siponimod lowers the number of lymphocytes, which may increase the risk of serious infections. Lymphocyte levels will be monitored by measuring a Complete Blood Count with differential at each in-clinic study visit.

+ *Liver Injury*

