terminations will also be indicated to the DSMB in a timely manner. The IRB will be notified per Barrow Neurological Institute IRB Policy regarding Adverse Events Reporting.

- Complaint Handling

The investigator or his/her designee is responsible for handling the following aspects of the product complaint process in accordance with the instructions provided for this study:

- recording a complete description of the product complaint reported and any associated AEs using the study-specific complaint forms provided for this purpose.
- informing the medical monitor within 24-48 business hours of subject complaints.

- Safety Measures

+ Routine Clinical Laboratory Tests

Routine hematology, blood chemistry will be performed at screening and subsequent follow-up visits as described in the schedule of events.

+ Electrocardiograms

For each subject, 12-lead digital electrocardiograms (EKGs) will be collected according to the Schedule of Events. The EKG at screening will be a single EKG and will be interpreted by the principal investigator, or sub-investigator. Every effort will be made to obtain EKGs around the same time of day; however, if unable to schedule for the same time, EKGs will still be completed per protocol. Patients must be supine for approximately 5 to 10 minutes before EKG collection

. EKGs will be interpreted by the principal investigator, or sub-investigator, with every effort made to have EKG results reviewed as close to time of collection as possible. Ideally EKG result review will be completed while the subject is still at site, so that any clinically relevant findings are identified with subject present.

After enrollment, if a clinically significant increase in the QT/corrected QT (QTc>500) interval from baseline, or other clinically significant quantitative or qualitative change from baseline, is present, the investigator will assess the subject for symptoms (for example, palpitations, near syncope, syncope) and to determine if the subject can continue in the study. The investigator, or qualified designee, is responsible for determining if any change in patient management is needed and must document their review of the EKG printed at the time of evaluation along with the final overread EKG and any alert reports.

+ Physical Examination

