Summary statistics for actual values and for changes from baseline will be tabulated for laboratory results by scheduled visit. Subjects with clinical laboratory values outside of the normal reference range at any post-baseline assessment will be summarized. Shifts from baseline laboratory values (to worst severity per subject) will be tabulated.

- Electrocardiogram Results

The EKG parameters (heart rate, PR interval, QRS interval, QT interval, and QTc interval) at each time recorded (scheduled for screening and study end) as well as the change from screening will be summarized with descriptive statistics.

The overall EKG assessment will be reported as “Normal” or “Abnormal” with respect to relevant abnormalities by the investigator. A shift table comparing the EKG assessment over the treatment period (every abnormal) to screening will be presented.

- Vital Signs

The observed data at baseline and change from baseline for each measurement day will be summarized with descriptive statistics.

BASELINE DESCRIPTIVE STATISTICS

The distributions of patients completing each study visit and the reason for early terminations will be tabulated for each treatment group. The duration of double-blind treatment within each treatment group and compliance rates will be summarized by descriptive statistics (mean, standard error, standard deviation, median, minimum, maximum, and sample size) for days of treatment, for total days of exposure, and by the distributions of patients exposed to various durations of treatment categories. Demographic and baseline characteristics will be summarized by descriptive statistics for all patients in each treatment group.

PLANNED INTERIM ANALYSES

Formal interim analyses are not planned. Data will be reviewed by the DSMB for their assessment of safety and risk/benefit considerations.

SUB-GROUP ANALYSES

No sub-group analyses are planned.

TABULATION OF INDIVIDUAL PARTICIPANT DATA

Participant data will be listed by measure and time point.

EXPLORATORY ANALYSES

Statistical analysis of the exploratory CSF, blood, and saliva biomarkers will be carried out by our biostatistician. Comparisons will assess the change from baseline for the following markers assessed at the frequency indicated in the schedule of visits Table 1):

- Alzheimer's Disease Cooperative Study- Activities of Daily Living (ADCS-ADL)
- blood inflammatory markers (e.g., TNF- α , IL-1 β , IL-6)
- CSF and plasma C-reactive protein
- CSF and plasma TNF- α

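### The EKG analysis text misstates the schedule and takes change from screening, so acute PR, QRS and QT/QTc change at each dose step has no direct summary by arm; separately, section 3.1.3 and Exclusion 1 disagree on cardiac drugs

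*Protocol*

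**What the plan says.** **EKG analysis.** Section 12, Safety Analyses, Electrocardiogram Results, states that heart rate, PR, QRS, QT and QTc "at each time recorded (scheduled for screening and study end) as well as the change from screening will be summarized with descriptive statistics". The shift table of normal/abnormal assessments over the treatment period is also set against screening.

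**EKG collection.** Section 10 says that "12-lead digital electrocardiograms (EKGs) will be collected according to the Schedule of Events". For the Baseline visit, section 1.1 specifies "EKG to be completed at pre- and 6-hours post-dose". Subjects having a lumbar puncture are dosed at Visit 2.5, with the same pair. Visits 3, 4 and 5, where the dose rises, each carry "EKG (pre-dose, post-dose at 6-hours". Single EKGs follow at Visits 6 to 14 and End of Study. The screening window is "Visit 1, Day -56 to 0 Screening Visit (Up to 8 weeks").

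**Other references in the same protocol.** For laboratory data: "Summary statistics for actual values and for changes from baseline will be tabulated for laboratory results by scheduled visit". For vital signs: "The observed data at baseline and change from baseline for each measurement day will be summarized with descriptive statistics". The QTc action rule in section 10 (Electrocardiograms) also judges the increase from baseline.

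**Why these EKGs are taken.** Section 3.1.1 places bradycardia and conduction delay first among the potential serious events: "Siponimod may cause the heart rate to slow, especially after taking the first dose". It gives the 6-hour EKG and hourly blood pressure and heart rate as the mitigation.

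**Cardiac drugs.** The lead sentence of Drug Interactions in section 3.1.3 makes the classes below it exclusions. The bullets are milder: one advises against starting siponimod, as a rule, with arrhythmogenic QT-prolonging or rate-lowering drugs, and another asks only for caution with beta-blockers. Exclusion 1 lists amiodarone and no other drug named there. Prohibited Concomitant Therapy in section 8 refers back to the exclusion list and adds no cardiac class.

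**The concern.** Safety is the primary endpoint and EKGs are one of its named components. The four pre-dose/6-hour pairs are placed around the drug's best-known acute effect. A summary meant to show that effect should compare the 6-hour tracing with the one taken that morning. The protocol instead fixes a reference that may be weeks older, and describes the schedule in a way that its own visit lists contradict. A report written to this text could omit the typical size, spread and extremes of the acute change in conduction and repolarisation at each dose step, in an age group for which section 6 (Justification for Dose) says there is no literature on siponimod's cardiac effects.

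The drug-list mismatch bears on the same risk from the eligibility side. A patient taking sotalol or diltiazem passes Exclusion 1, although section 3.1.3 treats the class as exclusionary.

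**Working it through.** **1. Count of scheduled EKGs** (section 1.1 visit lists and the EKG row of Table 1)

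- Screening: 1
- Baseline and Visits 3, 4, 5, pre-dose and 6-hour: 4 × 2 = 8
- Visits 6 to 14: 9
- End of Study: 1
- Total: 1 + 8 + 9 + 1 = 19 tracings, at 1 + 4 + 9 + 1 = 15 visits

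On drug: Baseline post-dose 1 + Visits 3–5 (3 × 2 = 6) + Visits 6–13 (8) = 15. A subject who has a lumbar puncture could have one more tracing, because dosing moves to Visit 2.5.

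The parenthesis in section 12 names 2 occasions, so it leaves out 19 − 2 = 17. The plan's stated schedule cannot be reproduced.

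**2. Age of the reference** (window opening at Day −56, nominal visit days)

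| Dose step | Longest gap from screening EKG | Gap from same-day pre-dose EKG |
|---|---|---|
| Day 1 | 1 + 56 = 57 days | 6 hours |
| Day 14 | 14 + 56 = 70 days | 6 hours |
| Day 28 | 28 + 56 = 84 days | 6 hours |
| Day 42 | 42 + 56 = 98 days | 6 hours |

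These are maxima, not expected values. At Visits 3 to 5, change from screening is also the sum of the previous dose's effect and the new step's effect.

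**3. Pairs available**

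4 × 105 = 420 planned: 4 × 70 = 280 on siponimod and 4 × 35 = 140 on placebo. Dropout lowers this; replacing subjects who stop before Visit 7 raises it.

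**4. Can the same-day change be read from screening-based tables?**

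Let the pre-dose and 6-hour changes from screening have a common SD *s* and correlation *r*. For paired subjects the mean same-day change is the difference of the two tabulated means, so it can be recovered. Its SD is *s* × √(2(1 − *r*)), and *r* would not be tabulated. The protocol gives no value, so *r* is an assumption: *r* = 0 gives 1.41*s*, *r* = 0.5 gives 1.00*s*, *r* = 0.9 gives 0.45*s*. Median and extremes cannot be recovered at all.

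**5. Cardiac drugs**

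Named as examples in section 3.1.3: quinidine, procainamide (Class Ia); amiodarone, sotalol (Class III); verapamil, diltiazem; ivabradine, digoxin. That is 2 + 2 + 2 + 2 = 8, plus beta-blockers as a class. In Exclusion 1: 1, amiodarone.

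**The case against.** The strongest reply on the EKG text is that the parenthesis is a drafting slip. The governing words cover every recorded time, section 10 sends collection to the Schedule of Events, the shift table spans the treatment period, and individual data are to be listed by time point. This stands. A reader might infer that on-drug EKGs will not be analysed; the documents do not support that, since only a strictly literal reading of the parenthesis would leave them out.

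A second reply is that a screening EKG is drug-free and the same rule applies to both randomised arms. This also stands: the choice does not bias the comparison between arms. It costs precision and does not isolate each dose step. Change from a drug-free reference at Visits 3 to 5 is a legitimate summary of cumulative effect and should be kept.

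Third, a reader might infer that first-dose heart-rate slowing goes unexamined or that patients are unprotected. Neither follows. Heart rate is taken hourly for six hours at each dose step, vital signs are analysed against baseline, and at the first dose the 6-hour EKG is reviewed before the patient leaves. But vital signs carry no PR, QRS or QT/QTc, so the gap narrows to those intervals.

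A SAP could add a same-day table. The protocol nonetheless fixes screening as the reference, so this is a stated choice and not a detail left open.

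On the drugs, the bullets are advisory, Exclusions 9 and 10 remove known heart block and recent coronary disease, and Exclusion 22 leaves room for investigator judgement. It would go too far to infer that such patients will be enrolled, or that beta-blockers are clearly allowed or clearly barred. The text supports only that the sections disagree.

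**Conclusion.** The point holds in a limited form and should be corrected. The protocol misstates the EKG schedule (2 occasions against 19 tracings at 15 visits) and makes EKG the exception by referring change and shifts to screening when laboratory results, vital signs and the QTc rule use baseline. The practical gap is the missing direct summary by arm of acute PR, QRS and QT/QTc change at four dose steps. The counts are for a completer on nominal days. The SD range rests on assumed correlations and equal SDs, and the conclusion does not depend on it.

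The eligibility mismatch is a separate and real contradiction: 1 of 8 named cardiac drugs appears in Exclusion 1, with beta-blockers unresolved. The eight are examples, not a closed list.

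**What to change.** **EKG analysis (section 12)**

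- Replace the parenthesis with wording such as *at each EKG in the Schedule of Events, including pre-dose and 6-hour post-dose*.
- Use the pre-dose EKG on Day 1 (or Visit 2.5) as the reference for change at all post-dose times and for the shift table. This keeps the cumulative change at Visits 3 to 5.
- Add the same-day pre-dose to 6-hour change by arm at Baseline/Visit 2.5 and Visits 3 to 5.

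Cost: corrected wording and a few extra tables from data already collected.

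**Eligibility (separate item)**

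- Bring section 3.1.3, Exclusion 1 and Prohibited Concomitant Therapy into line. List as excluded Class Ia and III anti-arrhythmics, arrhythmogenic QT-prolonging drugs, and heart-rate-lowering drugs such as verapamil, diltiazem, ivabradine and digoxin.
- Have the sponsor state whether beta-blockers are excluded, as the lead sentence implies, or allowed with caution, as the bullet says. That is a clinical decision.

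Cost: an amendment to the eligibility text and a slightly narrower eligible pool.

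### EKG change and the EKG shift table are referenced to a screening recording up to 8 weeks before first dose, although a Day 1 pre-dose EKG and same-day pre-dose/6-hour pairs are scheduled

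*Protocol*

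**What the plan says.** Protocol section 12, Safety Analyses, Electrocardiogram Results, covers heart rate, PR, QRS, QT and QTc. Values are to be shown "at each time recorded (scheduled for screening and study end"), and these "as well as the change from screening will be summarized with descriptive statistics". For the investigator's overall normal/abnormal reading, "A shift table comparing the EKG assessment over the treatment period (every abnormal) to screening will be presented". Screening is therefore the stated reference for both outputs.

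Section 1.1 places that visit at "Visit 1, Day -56 to 0 Screening Visit (Up to 8 weeks"). The same section schedules more EKGs around dosing:

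- Visit 2 (Baseline, Day 1): "EKG to be completed at pre- and 6-hours post-dose".
- Visit 2.5, which replaces Day 1 dosing for participants who have a lumbar puncture at Baseline: "EKG (pre-dose and post-dose at 6 hours", with a 10-minute tolerance.
- Visits 3, 4 and 5, the three dose-increase visits: again pre-dose and 6 hours post-dose.
- Each later clinic visit, through to the end-of-study visit: one EKG.

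In the same part of section 12, laboratory results and vital signs are summarised as changes from baseline.

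**The concern.** Safety is the primary endpoint, and EKGs are one of its named components (synopsis, Endpoints). Section 3.1.1 lists bradycardia and conduction delay first among the potential serious events, ties them especially to the first dose, and names the 6-hour EKG as a mitigation. The section on dose justification says there is no literature on siponimod's cardiac adverse events in people over 60. The EKG tables are therefore among the more informative safety outputs of this trial.

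An acute effect at 6 hours is a within-day contrast. The trial collects the recordings that measure it directly, yet the stated analysis compares everything with a recording that may be weeks older. Two things follow.

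1. Whatever happens between screening and Day 1 (an intercurrent change, a medication change, ordinary variation) enters the change and can enter the shift table as if it belonged to treatment.
2. The acute change carries more noise than it needs to.

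The protocol states screening as the reference, so this is not a detail left open for a statistical analysis plan to fill.

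**Working it through.** **No figure to reproduce.** The protocol gives no EKG SD, correlation, precision target or planned test. The check is of text against text, followed by an illustration.

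**Step 1: age of the reference.** The earliest screening day is -56, and visits after Day 1 have a window of +7 days. Maximum age = visit day + window + 56.

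| Visit | Calculation | Maximum age of screening EKG |
|---|---|---|
| Day 1 | 1 + 56 | 57 days |
| Visit 3 | 14 + 7 + 56 | 77 days |
| Visit 4 | 28 + 7 + 56 | 91 days |
| Visit 5 | 42 + 7 + 56 | 105 days |

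The reference is about 8 weeks old at most at first dose, and older at each dose increase. A same-day pre-dose EKG is about 6 hours old at the post-dose reading.

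**Step 2: references side by side.**

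| Measure | Reference in section 12 |
|---|---|
| Laboratory values | Baseline |
| Vital signs, including pulse | Baseline |
| EKG parameters | Screening |
| EKG normal/abnormal shift | Screening |

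Pulse as a vital sign and heart rate on the EKG are thus referenced to different days.

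**Step 3: the shift table.** Take a participant whose EKG is normal at screening, abnormal on Day 1 before dosing, and still abnormal on treatment. Referenced to screening, this is a shift from normal to abnormal over the treatment period. Referenced to the Day 1 pre-dose EKG, it is no shift. Section 12 defines a treatment-emergent adverse event as one that first occurs or worsens after study drug, so the shift table departs from the rule used for adverse events.

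**Step 4: precision, as illustration.** Let s be the SD of a single reading, equal at both times, and rho the correlation between the two readings. Then

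Var(change) = 2 s² (1 − rho),

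and the ratio of variances is (1 − rho_screening) / (1 − rho_same-day); s cancels.

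Assume rho_screening of 0.5-0.7 and rho_same-day of 0.7-0.85. Taking the ends of both ranges:

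- Smallest ratio: (1 − 0.7) / (1 − 0.7) = 0.30 / 0.30 = 1.0
- Largest ratio: (1 − 0.5) / (1 − 0.85) = 0.50 / 0.15 = 3.3

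On the SD scale this is √1.0 = 1.0 to √3.3 = 1.8. A second assumed set (screening 0.5-0.8, same day 0.8-0.9) gives SD ratios from √(0.2/0.2) = 1.0 to √(0.5/0.1) = 2.2. No precision is lost only where the screening correlation is as high as the same-day one.

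**Step 5: which EKGs are covered.** The parenthesis in the analysis text names screening and study end only. The visit text and Table 1 schedule EKGs at every clinic visit. Read literally, the parenthesis leaves out the 6-hour recordings altogether. If instead the words before it cover every EKG, pre-dose and 6-hour means would both be tabulated. The mean acute change could then be had by subtraction, but without its within-participant spread, and the shift table would be unchanged. Footnote h to Table 1 mentions only the 6-hour EKG; the visit text states the pre-dose one as well.

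**The case against.** The other side has several good points.

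- **The arm comparison is not biased.** Randomisation takes place at Day 1, after the screening EKG, so drift before treatment falls on both arms alike in expectation. The analysis is descriptive and no EKG test is planned. This stands. A reader might infer a distorted treatment comparison; the documents do not support that.
- **Acute heart rate has a second source.** Vital signs are taken pre-dose and hourly for 6 hours on Day 1 and at Visits 3-5, and are analysed from baseline. This stands, and it limits the acute loss chiefly to PR, QRS and QTc. A reader might infer that first-dose heart-rate slowing would be obscured; that goes too far.
- **Participants are protected regardless.** The Day 1 6-hour EKG is reviewed before the participant leaves, adverse events are tabulated and individual data are listed. This stands, but none of it replaces a correct group summary.
- **The size is assumed.** A variance ratio of 1.7-2.0 is tempting, but it appears only when low correlations are paired with low and high with high: 0.5/0.3 = 1.7, 0.4/0.2 = 2.0, 0.3/0.15 = 2.0. Nothing justifies that pairing.
- **Two supporting arguments add little.** Section 10 says "The EKG at screening will be a single EKG", but no replicates are planned pre-dose on Day 1 either. Section 10 also has the investigator act "if a clinically significant increase in the QT/corrected QT (QTc>500) interval from baseline", but does not define baseline there, and section 11 treats conditions present at screening as baseline. No contradiction with individual review is established.
- **One outdated sentence may explain everything.** A design with EKGs only at screening and study end would have screening as its sole pre-treatment value. That is plausible, and it is a reason to correct both in one edit rather than to leave the reference as it is.

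The stated reference, the misplaced shifts and the avoidable noise remain.

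**Conclusion.** The point holds in a limited form. The protocol fixes screening as the reference for EKG change and shift, although a better reference is already scheduled and its own laboratory and vital-sign analyses use baseline. The certain consequence is in the shift table: an abnormality that arises between screening and Day 1 and persists is credited to the treatment period, in either arm. The second consequence is extra between-day variation in the acute change, mainly for conduction and QTc intervals.

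The amount of extra variation cannot be taken from the documents. The 1.0 to 3.3 range for the variance ratio rests wholly on assumed correlations and includes no loss at all. This is a worthwhile correction to a descriptive safety analysis. It does not threaten the validity of the randomised comparison or the monitoring of individual participants.

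**What to change.** Amend the Electrocardiogram Results paragraph in section 12 in one edit:

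1. Define the EKG baseline as the Day 1 pre-dose recording (Visit 2, or Visit 2.5 for those dosed there), and use it for both change and the shift table. Use the screening EKG only if the pre-dose one is missing.
2. Add, by arm, the change from the same-day pre-dose EKG to the 6-hour EKG on Day 1 and at Visits 3, 4 and 5.
3. Replace the parenthesis on when EKGs are scheduled with a reference to the visit schedule, and let Table 1 footnote h mention the pre-dose EKG as the visit text does.

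Every EKG needed is already scheduled. The cost is analysis wording and a few extra table columns; no participant procedure and no clinical rule changes.
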